7.2 Demographic and Baseline Characteristics

Demographics will be summarized by randomized treatment group and for the FAS, Safety, PPP, and CP populations. The following characteristics will be summarized.

- Sex (Male, Female)
- Race (White, Black or African American, Asian, American Indian or Alaska Native, Native Hawaiian or Other Pacific Islander, Other)
- Ethnicity (Hispanic or Latino, Not Hispanic or Latino)
- Age
- Age group (50 65 years inclusive, > 65 years of age)
- Height
- Weight
- Body mass index

[figure not shown]
A summary of baseline characteristics will also include: MMSE group at screening (22-26, or >26), CDR-global (CDR-G), diagnosis of MCI or Mild AD, baseline values of all primary and secondary endpoints, use of concomitant AD medications (AChEI or none), in addition to height, weight, and body mass index. Baseline MMSE, calculated as the average of screening and V2 scores, will be summarized. Screening RBANS-delayed index score will also be summarized.

In addition, baseline values of hippocampal volume, cortical thickness, ventricular volume and whole brain volume will be summarized. For subjects in the plasma and CSF biomarker populations, the baseline values for the plasma and CSF core AD biomarkers will be provided when the analysis results become available.

The demographics and baseline characteristics will be summarized and tabulated by randomized treatment group.

7.3 Treatment Compliance

Overall treatment compliance will be calculated as a percentage using the total number of tablets that were dispensed and returned. Patients will be grouped into categories of < 70%, < 80%, 80% to 125% (inclusive), > 125%. Counts will be summed over the visits for each patient to calculate an overall compliance value.

Compliance = (# of tablets dispensed - # of tablets returned) / # of tablets that should have been taken \times 100%

For the calculations, the formulas are based on the assumption that patients take 2 tablets per day except for the clinical visit days.

- Number of tablets dispensed = number of kits × Number of cards per kit × 16. A Sevencard kit is to be dispensed during titration Visit 2/Baseline and 5-card kits are to be dispensed for rest of the visits.
- Number of tablets should have taken = Number of days between visits × 2 Number of clinical visits (subject will only take one tablet during clinical visit days). See Table 1 below for details of dispensation information.

 Table 1
 Dispensation Schedule

Visit	Kit Type	# of Kit to	# of Blister cards	# Tablets
		Dispense	per kit	per Card
Visit 2 - Baseline	ALZ-801 265mg	1	7 cards per kit	16
	Titration			
	Placebo Titration	1	7 cards per kit	16
Visit 4 – Week 6	ALZ-801 265mg	2	5 cards per kit	16
	Placebo	2	5 cards per kit	16
Visit 5 – Week 13	ALZ-801 265mg	3	5 cards per kit	16
Visit 7 – Week 26	Placebo	3	5 cards per kit	16
Visit 8 – Week 39				
Visit 9 – Week 52				
Visit 10 – Week 65*				
*No kits will be projected				
after this visit				

The number of tablets taken for kits that were not returned will be imputed to be the number of tablets that were dispensed.

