#### **Packaging**

ALZ-801 immediate-release tablets will be packaged as kits containing blister cards. Each blister card contains a 1-week supply with two blister strips, one for AM and one for PM dosing (8 tablets in each strip). The total number of tablets for a 1-week blister card is 16 tablets, for 7 days of dosing plus 1 day overage. The materials used for the blister strips are of standard commercial grade. The product contact side of this material conforms to FDA 21CFR175.300 and the Council of Europe Resolution AP (2004) and (EU) No. 10/2011.

Confidential Page 53 of 115

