6.3 Per Protocol Population (PPP)

The PPP will include all study subjects in the FAS population who are at least 80% compliant with study drug for the duration of their study participation without major protocol deviations that may impact primary or key secondary efficacy assessments. Membership in the PPP will be determined prior to database lock. The PPP will be used for supportive analyses of the primary and key secondary efficacy endpoints.

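### SAP 7.3 counts every tablet in an unreturned kit as taken, surplus included, so some non-adherent subjects can cross the Per Protocol Population's 80% floor

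*SAP*

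**What the plan says.** SAP 7.3 (Treatment Compliance) defines the measure as "Compliance = (# of tablets dispensed - # of tablets returned) / # of tablets that should have been taken", as a percentage, with counts summed over visits. The dispensed count is "Number of tablets dispensed = number of kits × Number of cards per kit × 16". Tablets due are two per day, with one on clinic days. For missing returns the rule is: "The number of tablets taken for kits that were not returned will be imputed to be the number of tablets that were dispensed".

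Supply exceeds need in two ways. Protocol 6.1.1 (Packaging) builds in spare tablets: "The total number of tablets for a 1-week blister card is 16 tablets, for 7 days of dosing plus 1 day overage". SAP Table 1 also issues more cards than weeks: one seven-card kit at Baseline for 6 weeks, two five-card kits at Week 6 for 7 weeks, and three five-card kits at each later dispensing visit for 13 weeks.

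SAP 6.3 uses the score for membership: "The PPP will include all study subjects in the FAS population who are at least 80% compliant". It sets no upper limit. It also requires no major protocol deviation that may affect the primary or key secondary efficacy assessments. The PPP is supportive for those endpoints.

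Protocol 6.3 tells subjects to return all cards at each visit, and Protocol 6.4 assesses compliance by counting returned tablets.

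**The concern.** When a kit does not come back, the returned-tablet count that measures adherence is missing. The SAP fills the gap with the largest possible value, which is more than a fully adherent subject could have been due to take. The numerator carries the surplus and the denominator does not.

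The PPP analysis is meant to show the effect in subjects who took the drug. If the rule lifts subjects below 80% above that line, the PPP includes some of those it was defined to leave out. The compliance table is inflated for the same reason. Nothing in either document caps the score, flags unreturned kits, or sets an alternative rule for them.

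**Working it through.** The documents report no compliance result, so there is no figure to reproduce. The inputs are SAP 7.3, SAP Table 1 and the visit days (Day 1 to Day 547, 546 days).

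**Dispensed and due, by interval.** Dispensed = kits × cards × 16. Due = 2 × days − 1 clinic day.

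| Interval | Dispensed | Due | Score if wholly unreturned |
|---|---|---|---|
| Baseline to Week 6 (42 days) | 1×7×16 = 112 | 83 | 134.9% |
| Week 6 to 13 (49 days) | 2×5×16 = 160 | 97 | 164.9% |
| Each 13 weeks (91 days), five times | 3×5×16 = 240 | 181 | 132.6% |
| Full course | 112+160+5×240 = 1472 | 83+97+5×181 = 1085 | 135.7% |

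The minus sign before the clinic-visit count is not visible in the SAP text as read, so the deduction is an assumption. Deducting all eight clinic days gives 2×546 − 8 = 1084 due (135.8%). With no deduction it is 1092 (134.8%). The one-day overage alone would give 16/14 = 114%, so the spare cards account for the rest.

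**Visit windows.** Stretching each interval to its limit gives 112/97 = 115.5%, 160/139 = 115.1% and 240/237 = 101.3%. All remain above 100%.

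**Partial non-return, full course.** Score = (tablets dispensed in unreturned intervals + true adherence × tablets due in the others) / tablets due. The figures use 1084 due and take the last 13-week supplies as unreturned, with 180 due in the final interval.

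- True 70%, one supply: (240 + 0.7×904)/1084 = 872.8/1084 = **80.5%**.
- True 50%, one supply: (240 + 0.5×904)/1084 = 692/1084 = 63.8%.
- True 50%, two supplies: (480 + 0.5×723)/1084 = 841.5/1084 = 77.6%.
- True 50%, three supplies: (720 + 0.5×542)/1084 = 991/1084 = **91.4%**.

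With 1085 due, the two bold figures become 80.4% and 91.3%, and the conclusion is the same.

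**Whole supplies skipped.** A subject who skips and keeps two 13-week supplies but takes everything else has true adherence of (1085 − 362)/1085 = 67% and scores (723 + 480)/1085 = 111%.

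**Single kits.** Suppose a true 70% taker leaves the third kit (80 tablets) untouched and unreturned. In one interval the score is (758.8 + 80)/1084 = 77.4%; in two it is (758.8 + 160)/1084 = 84.8%.

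**Where these scores land.** 80.5%, 91.4% and 111% all fall in the SAP's 80% to 125% category, so the compliance table would not reveal them. A subject who returns nothing falls in the >125% category, which is visible but does not bar PPP entry.

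**The case against.** The strongest reply is that little depends on the rule. The primary analysis uses the Full Analysis Set under a treatment-policy strategy and makes no use of compliance, nor does the multiplicity procedure. The PPP is one of several supportive analyses, beside the completer and while-on-treatment analyses. The rule is the same in both blinded arms. This stands, and it limits the point to the compliance table and the PPP results.

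A second reply is that SAP 6.3 has another criterion. Missed doses and regimen deviations must be recorded (Protocol 6.2.2 and 6.4), reasons given for unaccounted tablets (Protocol 6.3), and deviations, including study-drug deviations, reviewed to select analysis subsets (SAP 7.4). A subject off drug for months could be excluded that way. This stands in part: SAP 7.4 says some deviations may not be major, and neither document links unreturned kits to PPP membership.

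A reader might infer that every subject who skips doses and keeps kits scores above 100% and enters the PPP. The arithmetic does not support that: over a full course, a true 50% taker with one or two unreturned supplies scores 63.8% or 77.6% and is excluded. A reader might also infer that non-return marks poor adherence. The documents give no evidence either way, and adherent subjects may throw away empty cards. The over-crediting of surplus tablets does not depend on that link.

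**Conclusion.** The rule is wrong as written and should be changed, but its reach is limited. A wholly unreturned interval scores above 100% regardless of intake (about 133% to 165% at scheduled visit times), and a full course with nothing returned scores about 136%. Some subjects below 80% are carried over the PPP floor: a true 70% taker with one unreturned 13-week supply (80.5%) and a true 50% taker with three (91.4%). Others are not, and the major-deviation criterion may remove some who are.

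The adherence patterns are illustrative assumptions: constant intake, or complete skipping of whole supplies. The documents give no rate of non-return, so the number of subjects affected and any shift in the PPP estimate cannot be stated. The primary analysis is unaffected.

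**What to change.** **SAP 7.3.** Treat the count for an unreturned kit as unknown, and remove that dispensing interval from both numerator and denominator. Leave credit on returned intervals uncapped; a cap at tablets due would empty the >125% category, which shows apparent over-use.

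**SAP 6.3.** Removal alone is not enough. The subject who skips and keeps two supplies would score 723/723 = 100% on what remains, and a subject who returns nothing would have 0/0. So require both:

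- at least 80% compliance on intervals with known counts; and
- known-count intervals covering a stated minimum share of tablets due.

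A share of 80% is one choice. It allows one unreturned 13-week supply (904/1085 = 83%) but not two (723/1085 = 67%). Subjects with no known counts are not in the PPP.

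**Reporting.** Tabulate unreturned kits by arm, and repeat the PPP analysis with unreturned tablets counted as not taken. The repeat is needed because a subject at 80% on 904 known tablets who took none of the other 181 would still qualify, with true adherence of 0.8×904/1085 = 67%.

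**Cost.** Wording in two SAP sections, one derivation, one table and one repeated analysis, all settled before database lock, when PPP membership is fixed. The PPP becomes slightly smaller and may lose some adherent subjects who discarded their cards.

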7.4 Protocol Deviations

Protocol deviations by treatment will be listed and summarized for the FAS Population. The protocol deviations will be reviewed by clinical and statistical teams to select appropriate analysis subsets.

Protocol deviations include, but are not limited to:

- Inclusion/Exclusion Criteria
- Study Drug Overdose

- Other Study Drug Deviation
- Visit Window
- Restricted Concomitant Medication Change
- Study Procedure
- Other

Note that some of these deviations may not constitute major deviations from the protocol and hence, subjects with these deviations may not necessarily be excluded from the Per-Protocol Population.

7.5 Prior and Concomitant Medications

The number and percent of prior and concomitant medications will be provided by the treatment groups used for the safety analyses. A concomitant medication is defined as any medication that is taken after administration of the first dose of study drug (i.e., after receiving study drug at the Baseline Visit). Prior concomitant medications are defined as medications that are started before administration of the first dose of study drug and continue beyond that date. New concomitant medications are defined as medications that are started on or after the first dose of study drug, including those started in the Safety follow-up period. Prior medication is defined as any non-study medication that starts and stops before the first dose of study drug. Partial dates will be imputed using rules in Section 7.1.5.

Prior and concomitant medications will be coded using WHO Drug Dictionary (most current version). Summaries will be provided by anatomical therapeutic chemical classification (ATC) and preferred term.

7.6 Medical History

[figure not shown]
Medical history will be summarized by SOC and PT based on randomization and will be presented in the listings. Summary tables will be provided for the frequency and percentage of patients.

8 STATISTICAL METHODS OF ANALYSIS

8.1 General Considerations

Efficacy and Safety analyses will be performed with the FAS and Safety/ITT populations, respectively. Data will be summarized overall and by treatment arms. All Case Report Form (CRF) data collected during the study will be presented within data listings.

Should any of the statistical methods proposed prove unsuitable during the final analysis, more appropriate methods will be used, and any changes will be documented in the clinical study

Following the International Council for Harmonisation (ICH) Guideline E9 (R1), an addendum adopted in November 2019, the estimand and its estimator and estimate will be defined for primary endpoint where inferential statistical comparison and hypothesis testing related to a treatment effect are of interest. When analyzing the efficacy endpoints, effort will be made to distinguish intercurrent events from non-informative withdrawals, as well as applying various sensitivity analyses to assess the robustness of the estimate(s) for the pre-specified estimands. The definition of an intercurrent event is, "events that occur after treatment initiation and either preclude observation of the variable or affect its interpretation", e.g., use of rescue or prohibited medications, changes in permitted medications, switching treatments, discontinuing treatments, and subject deaths. Details on estimands, estimators, estimates, and intercurrent events are discussed in endpoint analysis section.

8.1.1 Descriptive Statistics

For descriptive statistical summaries, the continuous variables will be summarized by number of observations (n), mean, standard deviation (SD), standard error (SE), median, minimum (MIN), and maximum (MAX). Descriptive statistics for biomarkers will include percent coefficient of variation (%CV). For categorical variables, frequency and percentage of subjects in each category will be provided.

Minimum and maximum values will be rounded to the precision of the original value. Means and medians will be rounded to one decimal place greater than the precision of the original value. SDs, SEs, and 95% confidence intervals (CIs) will be rounded to two decimal places greater than the precision of the original value. Percentages for summarizing categorical data will be rounded to one decimal place. P-values, if needed, will be presented with 4 decimal places and values less than 0.0001 will be presented as <.0001.

The by-subject listings, including data at scheduled and unscheduled visits, will be sorted by treatment arm, subject ID, and then by date/time of the records.

8.1.2 Hypothesis Testing

[figure not shown]
The Null Hypothesis of the study is that the CBL of ADAS-Cog 13 in ALZ-801 arm is not different from the placebo arm at 78 weeks.

The Alternate Hypothesis is that the CBL of ADAS-Cog 13 (Mohs 1997) in ALZ-801 arm is different from the placebo at 78 weeks.

The statistical testing will be two-sided and will be performed at the α =0.05 significance level. The key secondary efficacy endpoints will be compared only after the comparison of the primary endpoint has reached statistical significance. The comparisons of key secondary

endpoints will be done using a graphical approach (Bretz 2009) that strongly controls the family-wise Type 1 errors arising from multiple comparisons (Figure 2).

Figure 2 Graphical Approach Procedure for Analysis of Key Secondary Outcomes

[figure not shown]
8.1.3 Definition of Study Baseline

Unless otherwise specified, baseline is defined as the last non-missing measurement obtained prior to the first dose of the study drug for all efficacy and safety measures. Values at screening visits that are the baseline for efficacy assessments will be summarized, and all other screening values will be presented in listings. The MMSE baseline is defined as the average of the scores at the screening visit and V2 visit. If the MMSE score is available from only 1 pre-dose visit (either screening or V2), that score will be used as the baseline value.

8.1.4 Handling of Multiple Observations

For clinical efficacy data, if multiple measures were recorded for the same protocol defined visit, the later (repeated) measure will be used for data summary and analysis. Repeated data from unscheduled visits will be treated similarly.

If a subject has a scheduled visit, the assessment obtained at the scheduled visit will be used for data summary and analysis. Otherwise, if no scheduled visit assessment exists but at least one unscheduled visit assessment is available within the protocol-defined visit window, then the data at the latest unscheduled visit within the protocol-defined visit window will be used for data summary and analysis. Furthermore, in cases where both an unscheduled visit assessment and an early terminated visit assessment exist within the same analysis window, the assessment from the early terminated visit will be utilized for summarization and analysis.

When a subject undergoes multiple scheduled MMSE screening measurements, the most recent assessment will be used as the screening score. Any previous records showing MMSE scores below 22 should be regarded as instances of screen failure.

8.1.5 Multiplicity of Secondary Endpoints

The graphical approach will be used on testing multiple endpoints in a predefined order to strongly control the family-wise type 1 errors arising from multiple comparisons (Bretz 2009). The alpha recycle is described in detail in Figure 2. For the primary efficacy endpoint (CFBL to week 78 in ADAS-Cog 13, i.e., H1) hypothesis testing, the initial 2-sided significance level is set to 0.05. Only if the H1 testing is successful will the next two key secondary endpoints: CFBL to week 78 in A-IADL (H2) and CFBL to week 78 in CDR-SB (H3), be tested each at an alpha level of 0.025. If H2 shows significance, its alpha level of 0.025 is passed on to H3 for testing at an endpoint-specific alpha level of 0.025+0.025=0.05. However, if H2 is not significant, H3 is still tested at the reserved alpha level of 0.025. In this scenario, if H3 turns out to be significant, the alpha level for H2 is recycled back for re-testing at 0.05.

Since a graphical approach is used in the analysis, the overall type I error rate is strongly controlled at the 2-sided α =0.05. The hypothesis testing for the additional clinical endpoints (not presented in Figure 2) will be done without control for type I errors due to multiple comparisons and the p-values will be considered nominal.

8.2 Visit Windows and Efficacy Data Algorithms and Definitions/Handling of Dropouts or Missing Data

8.2.1 Visit Windows

Data at scheduled visits will be assigned to analysis visits as defined in the Analysis Visit Window tables below (Table 2, Table 3, Table 4, Table 5, Table 6, Table 7), to ensure that all visits have the potential to be included in the summaries. The unscheduled visits on or before day 1 will be mapped according to scheduled assessments. Visit windows herein will also be used to classify unscheduled and early termination visits.

For volumetric MRI measures (vMRI), if multiple measures were recorded for the same protocol defined visit, the later (repeated) measure will be used for data summary and analysis. If vMRI measures are missing for a protocol defined visit and an unscheduled vMRI measure is available, the unscheduled vMRI measure will be mapped to the closest missing protocol defined visit.

Table 2 Analysis Visit Windows for Assessments Done at Visit 4, 5, 7, 8, 9, 10, 11

Stage/Visit	Target Day	Study Days	
		Lower Bound	Upper Bound
Week 6 (Visit 4)	43	2	67

Stage/Visit Target Day		Stud	y Days
Week 13 (Visit 5)	92	68	137
Week 26 (Visit 7)	183	138	228
Week 39 (Visit 8)	274	229	319
Week 52 (Visit 9)	365	320	410
Week 65 (Visit 10)	456	411	501
Week 78 (Visit 11)	547	502	592

Table 3 Analysis Visit Windows for Assessments Done at Visit 5, 7, 8, 9, 10, 11

Stage/Visit	Target Day	Study Days	
		Lower Bound	Upper Bound
Week 13 (Visit 5)	92	2	137
Week 26 (Visit 7)	183	138	228
Week 39 (Visit 8)	274	229	319
Week 52 (Visit 9)	365	320	410
Week 65 (Visit 10)	456	411	501
Week 78 (Visit 11)	547	502	592

Table 4 Analysis Visit Windows for Assessments Done at Visit 4, 5, 7, 9, 11

Stage/Visit	Target Day	Study Days	
		Lower Bound	Upper Bound
Week 6 (Visit 4)	43	2	67
Week 13 (Visit 5)	92	68	137
Week 26 (Visit 7)	183	138	274
Week 52 (Visit 9)	365	275	456
Week 78 (Visit 11)	547	457	592

Table 5 Analysis Visit Windows for Assessments Done at Visit 5, 7, 9, 11

Stage/Visit	Target Day	Study Days	
		Lower Bound	Upper Bound
Week 13 (Visit 5)	92	2	137
Week 26 (Visit 7)	183	138	274
Week 52 (Visit 9)	365	275	456
Week 78 (Visit 11)	547	457	592

Table 6 Analysis Visit Windows for Assessments Done at Visit 7, 9, 11

Stage/Visit	Target Day	Study	y Days
		Lower Bound	Upper Bound
Week 26 (Visit 7)	183	2	274
Week 52 (Visit 9)	365	275	456
Week 78 (Visit 11)	547	457	592

Table 7 Analysis Visit Windows for Assessments Done at Visit 9, 11

Stage/Visit	Target Day	Study Days	
		Lower Bound	Upper Bound
Week 52 (Visit 9)	365	2	456
Week 78 (Visit 11)	547	457	592

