#### 7.2.14. Early Termination Visit

Early Termination is also considered an EOT visit. An ET Visit should be completed if a study subject discontinues prematurely from the study, or is discontinued from the study by the Investigator [see Section 5.5].

If a study subject prematurely discontinues from study treatment, an ET Visit should be conducted at the time of discontinuation. Every effort should be made to conduct all ET procedures as specified below and in the Schedule of Assessments [Appendix 2]. Every attempt should be made to follow study subjects who have an SAE for 4 weeks after their ET Visit. For subjects who continue to be followed for safety, SAEs should continue to be reported as described in [Section 8.4.2].

The following procedures will be performed. The recommended order is shown below:

- Vital signs (prior to blood draw)
- Physical examination
- Neurological examination
- Weight
- AE assessment
- Change in medications since last visit
- ADAS-Cog
- MMSE
- A-IADL
- CDR
- DAD
- NPI
- QoL-AD
- RUD Lite
- C-SSRS
- Single 12-lead ECG (triplicate if QTc prolongation observed previously or in current visit)
- Safety laboratory tests
- Plasma sample collection for biomarker assessment (exact time of sampling will be recorded)
- Plasma sample collection for PK assessment (exact time will be recorded)
- Urine for urinalysis
- Urine pregnancy test (female subjects of childbearing potential)
- Study drug dosing from the last dose prior to the visit (time of dosing will be recorded)

Confidential Page 78 of 115

- Study drug return, accountability, and compliance
- BP and pulse approximately 15 minutes after last blood draw
- MRI (as soon as possible, no later than 2 weeks after the ET visit)

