#### For subjects in the CSF sub-study:

- MRI should be performed and results available prior to LP.
- LPs should be performed via gravity drip method with atraumatic needles to reduce the risk of CSF leakage and post-LP headaches. This technique will allow for optimal biomarker collection and analysis.
- Site should schedule the LP as soon as possible, no later than 2 weeks after the MRI.
- CSF sample collection for biomarker assessment (exact time will be recorded)
- CSF sample collection for PK assessment (exact time will be recorded)

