6.10 CSF Biomarker Population

The CSF biomarker population will include all subjects with an evaluable baseline CSF biomarker sample who have received at least one dose of study drug and have at least one evaluable post baseline CSF biomarker sample. All CSF biomarker analyses will be performed on this population.

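### SAP Table 7 opens the Week 52 window at Day 2, so an early-termination CSF sample taken after only weeks on drug is analysed as a one-year biomarker value

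*SAP*

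**What the plan says.** - **Schedule.** The schedules of assessments (Protocol Appendix 2, SAP Appendix 1) place CSF sampling at baseline, Week 52, Week 78 and ET only. The one window table that fits is "Table 7 Analysis Visit Windows for Assessments Done at Visit 9, 11".
- **Window.** Its Week 52 row reads "Week 52 (Visit 9) 365 2 456": target day, lower bound, upper bound. In Tables 4 to 6 the corresponding row is "Week 52 (Visit 9) 365 275 456".
- **Scope.** SAP Section 8.2.1 states: "Visit windows herein will also be used to classify unscheduled and early termination visits". Its only marker-specific mapping rule is for volumetric MRI.
- **ET sample.** Protocol Section 7.2.14 allows the ET MRI up to 2 weeks after the ET visit and requires its result before the lumbar puncture. For CSF sub-study subjects: "Site should schedule the LP as soon as possible, no later than 2 weeks after the MRI".
- **Population.** SAP Section 6.10 admits a treated subject with an evaluable baseline sample and "at least one evaluable post baseline CSF biomarker sample". No minimum exposure is set.
- **Analysis.** SAP Section 8.4 analyses CSF change by MMRM with visit and treatment-by-visit terms. Change to Week 52 is a listed exploratory CSF endpoint in SAP Section 5.2.5.

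**The concern.** Take a subject who stops on Day 20. The MRI may follow by Day 34 and the lumbar puncture by Day 48. That sample reflects less than three weeks of dosing, the first two on the titration regimen, and up to four weeks off drug. Under Table 7 it becomes the subject's Week 52 value. No later CSF sample is planned to replace it, because the retrieved-dropout visits in Protocol Section 7.2.15 include no lumbar puncture.

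If the biomarker effect builds with time on drug, such samples pull the Week 52 treatment difference toward zero. They also enter the model that produces the Week 78 estimate: with any within-subject correlation, a mislabelled Week 52 value helps predict that subject's missing Week 78 value. At stake is what a reported Week 52 CSF result means, not the trial's confirmatory conclusion.

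**Working it through.** **1. Reproducing the window.** All bounds in Tables 2 to 7 follow one rule: the first post-baseline window opens at Day 2, inner bounds are midpoints between target days (rounded down), and the last window closes 45 days after its target.
- Table 7, Week 52 upper bound: (365 + 547)/2 = 456. The lower bound is Day 2, because Week 52 is the first post-baseline visit in that table.
- Tables 4 to 6, Week 52 lower bound: (183 + 365)/2 = 274, so the window starts at Day 275.
- Table 7's Week 52 window spans 456 − 2 + 1 = 455 days: 363 before target and 91 after. In Tables 4 to 6 the lower side is 365 − 275 = 90 days.

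**2. Inputs for size.**
- 60 sub-study subjects per arm and 20% dropout (Protocol Section 10.3.2). The SAP's expected 96 of 120 at Week 78 matches: 120 × 0.80 = 96.
- Assumptions: dropout is even over Days 2 to 547 (546 days); every dropout gives an ET lumbar puncture, on the ET day; and every other subject has a Week 52 sample, so there are 60 Week 52 records per arm.

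**3. Counts per arm.** Dropouts: 60 × 0.20 = 12.
- ET on Days 2 to 456: 12 × 455/546 = 10.0.
- ET on Days 2 to 274: 12 × 273/546 = 6.0, which is 6/60 = 10% of Week 52 records.
- ET on Days 2 to 91: 12 × 90/546 = 2.0.

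The other 4 (Days 275 to 456) have a mean day of (275 + 456)/2 = 365.5, which is on target, so they cause no dilution.

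**4. Dilution of the Week 52 difference.**
- Linear growth with time: the mean day of the early samples is (2 + 274)/2 = 138, and 138/365 = 0.378. Dilution = 0.10 × (1 − 0.378) = 6.2%.
- No effect at all in the early samples: 10%.
- With 17% dropout: 10.2 dropouts and 5.1 early samples per arm, 8.5% of records. Dilution is 0.085 × 0.622 = 5.3%, or 8.5% with no effect.

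**5. In standard errors.** The protocol assumed a 15 pg/mL difference in CSF p-tau181 at Week 78 and an SD of 25 to 30 pg/mL. I treat that SD as the SD of change, which the protocol does not say outright.
- Linear Week 52 effect: 15 × 365/547 = 10.0 pg/mL.
- SE of the difference at 60 per arm: SD × √(2/60), giving 4.6 (SD 25) to 5.5 (SD 30).
- Linear growth: a bias of 0.62 pg/mL, or 0.11 to 0.14 SE.
- No effect in early samples: a bias of 1.0 pg/mL, or 0.18 to 0.22 SE.

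The knock-on at Week 78 cannot be sized, because the documents give no within-subject correlation for CSF.

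**The case against.** **CSF is exploratory and unpowered in the SAP.** This stands. No primary or key secondary test uses CSF, and Week 52 is an intermediate timepoint. It limits the importance of the point but does not answer it.

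**Table 7 follows the same rule as the other tables.** Also true. Day 275 elsewhere is a midpoint with a Week 26 visit that CSF does not have, so Table 7 is not an internal contradiction. But opening at Day 2 is tolerable when the first visit is Week 6 or 13; with a first visit at Week 52, the lower side becomes 363 days.

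**Scheduled values take precedence (SAP Section 8.1.4).** That section opens with clinical efficacy data, but even applied to CSF it protects only subjects who have a scheduled Week 52 sample. An early terminator has none. The section limits unscheduled assessments to the protocol-defined window but sets no such limit for ET assessments.

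**The place of ET samples in the model is inferred.** SAP Section 8.4 names only baseline, Week 52 and Week 78 CSF as batched. Yet Section 8.2.1 classifies ET visits without exempting CSF, and the protocol collects the sample. At the least, the plan needs to say.

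**Narrowing the window gains no real precision and removes a pull toward zero.** Fair. Relative to a full set of Week 52 samples, signal to noise is about 0.94 now and √(54/60) = 0.95 after the change. Dropping early terminators leaves the estimate resting on those who stayed. The case is about what the Week 52 label means, and it is why the all-samples analysis should be kept alongside.

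**Conclusion.** The point holds as a labelling flaw in an exploratory analysis. Under SAP Section 8.2.1, an ET CSF sample from a subject with no scheduled Week 52 sample is analysed as Week 52 however early it was taken. The size is modest: at most about 6 samples per arm before Day 275, diluting the Week 52 difference by about 6% to 10%, or roughly 0.1 to 0.2 SE. This rests on 20% even dropout and complete ET sampling. Fewer ET lumbar punctures would lower it; earlier dropout would raise it.

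Five stronger readings are tempting and not supported:
- *Every CSF sample from Day 2 to Day 456 is relabelled.* Only subjects without a scheduled Week 52 sample are affected.
- *About 17% of Week 52 records (10 of 60) are compromised.* That counts the 4 per arm from Days 275 to 456, which average on target.
- *The active arm is hit harder because of nausea.* The withdrawal rate of about 5% in Protocol Section 2.2.3 is for tramiprosate; Section 2.3.1.2 reports ALZ-801 nausea as mild and transient. Imbalance is possible, not shown.
- *The error passes to Week 78 through an unstructured covariance.* That structure appears only in example code for the ADAS-Cog 13 multiple-imputation analysis. The CSF structure is not stated, though some carry-over follows from any within-subject correlation.
- *Treatment-policy handling justifies the rule.* The SAP states that strategy for the primary and secondary efficacy endpoints, not for CSF. In any case it would use a Week 52 measurement regardless of discontinuation; it does not turn a Day 30 measurement into one.

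**What to change.** - Add a CSF-specific window to SAP Section 8.2.1 with Week 52 at Days 275 to 456 (90 days before target, 91 after) and Week 78 unchanged.
- List ET CSF samples from before Day 275 by study day and days since last dose, outside the main by-visit model. No off-drug cut-off is proposed, since the documents give no basis for one.
- Report the analysis that includes them under the current Table 7 window as a named sensitivity analysis.
- State that subjects whose only post-baseline sample falls before Day 275 remain in the CSF biomarker population of Section 6.10 but contribute no record to the main model.
- Leave Table 7 in place for QoL-AD and RUD Lite. Review it and Table 6 (Week 26 from Day 2) separately, because they serve other endpoints.

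**Cost.** One added table and one sensitivity run. About 6 early ET samples per arm leave the main CSF model, and the Week 52 SE widens by about 5% (√(60/54) = 1.054). The change should be made before unblinding. The documents do not show whether that has happened; if it has, keep the planned analysis and report the narrower window as the sensitivity analysis.
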